Description of Study Intervention/Experimental Manipulation:	
The multisite study will utilize a SMART design. Suicidal college students seeking counseling services through the College Counseling Centers (CCCs) will be recruited.
 
In Stage 1, student participants will be initially randomized into either treatment as usual (TAU) or Collaborative Assessment and Management of Suicidality (CAMS). Student participants receiving TAU will receive the customary treatment they would receive at the CCC. Student participants receiving the CAMS intervention will receive CAMS through weekly sessions with a counselor that will last for 50-60 minutes.
 
Responders to either CAMS or TAU may stop treatment after 4 sessions (minimum dose of treatment), based on counselors' ratings

of improvement of students' symptoms of suicidality. Stage 1 has an intended duration of no more than 6 weeks.

Non-responders to Stage 1 treatments will be re-randomized to one of two Stage 2 treatments: CAMS or College Counseling Dialectical Behavior Therapy (CC-DBT). Student participants receiving CC-DBT will engage in individual therapy and either a skills training group or individual skills training. Stage 2 has an intended treatment duration of 1-8 weeks.

All treatment in Stage 1 and Stage 2 (TAU, CAMS, and CC-DBT) will be administered via a hybrid intervention model, either online or in person. For the purposes of these studies, a hybrid intervention model means that a student participant's course of care may be delivered completely via telehealth, completely in person, or via a combination of in person and telehealth sessions. Decisions about what type or format of sessions to hold will be made by the counselor and based on several factors: university policy, CCC policy, location of student/counselor participants, and preference of the student/counselor participants. Data will be collected on the number of sessions conducted via each modality (captured via EHR). Such data will be explored to inform more richly tailored ATSSs.

Counselors will provide TAU, CAMS, and CC-DBT to study participants. They will also participate in CAMS and CC-DBT trainings and ongoing consultation teams for each. In addition, counselors will complete questionnaires at regular intervals throughout their participation in the study.

Study Duration: The duration of the CAMPUS Trial is approximately 30 months (2.5 years) total duration from beginning of recruitment until final data collection.

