4.4 JUSTIFICATION FOR INTERVENTION

First Stage (Stage 1) of SMART Study (N=480): Randomization to TAU or CAMS (4-6 Weeks). After baseline, student participants will be randomly assigned to TAU (n= 240) or CAMS (n=240). Stage 1 treatment will last 4-6 weeks. We chose this treatment length because the average number of sessions at CCCs is 5.22 (with a median of 4 sessions),²¹ 6-8 CAMS sessions were enough to resolve SR in college students in an earlier trial,²⁷ and in our CAMPUS feasibility study, average number of Stage 1 sessions was 6. Student participants who appear to be deteriorating (worsening SI on the Counselor CGI-I scale) or who maintain high levels of SI without improvement may be re-randomized to Stage 2 early after session 4.

Student participants randomly assigned to TAU will receive the customary treatment they would receive at that CCC—on average, weekly individual therapy, but it may also occasionally include group participation and/or medication referral. Counselors conducting TAU treatment will be informed to do counseling as usual for a period of 4-6 weeks, except that counselors will be asked not to utilize CAMS or DBT strategies. The book entitled *“Collaborative Assessment and Management of Suicidality: Managing Suicidal Risk: A Collaborative Approach (2nd edition)”*⁷ will serve as the manual for CAMS treatment in Stage 1/Stage 2. CAMS individual sessions will be provided weekly for 50-60 minutes and will follow the Suicide Status Form.

Second Stage (Stage 2) of SMART Study (n≈240): Re-randomization to CC-DBT or CAMS (1-8 Weeks). The treatment length for Stage 2 was chosen based on previous studies with CAMS and DBT, ease of dissemination to CCCs later, and informed by data from the CAMPUS feasibility study. Based on previous CAMS studies,²⁷ our pilot study and CAMPUS feasibility study, we estimate that n≈240 of student participants will resolve their SR during Stage 1 and that n≈240 will be re-randomized to Stage 2.

DBT Individual Therapy. Participants will receive weekly individual teletherapy/in-person sessions with a CC-DBT-trained counselor for up to 8 weeks total. The DBT manual²⁹ guidelines such as orienting clients to the treatment model, using a diary card to monitor problematic behaviors, relying on a hierarchy of targets to guide treatment at each session, and conducting chain and solution analyses to determine and address controlling variables of problematic behavior will be followed.¹⁴⁵

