DBT Skills Training. The skills training sessions will follow the DBT Skills Training manual,^{8,29,144} but adapted to fit within a standard academic term (6 weeks). The skills training sessions will be provided via teletherapy/in person and will include skills from all four modules of skills acquisition (mindfulness, emotion regulation, interpersonal effectiveness, and distress tolerance), but with the following modifications: greater focus on emotion regulation given past research with college students,^{12,146} and fewer skills taught within each module. Depending on participant flow and time of the semester/quarter, skills training may be conducted individually or in group format.

Peer consultation team is an inherent part of DBT. Counselors will participate in weekly DBT consultation team meetings conducted remotely or in person.^{29,147} Phone/text skills coaching is viewed as essential for the generalization of DBT skills to the environment.²⁹ Counselors will coach their own student participants but, adapting to this setting, they will be encouraged to observe their own limits and comply with local CCC policies/legal requirements, as warranted.

Hybrid Intervention Model

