6.1.6 ADMINISTRATION AND/OR DOSING

Treatment dosage for Stage 1 will consist of prescribed weekly sessions for up to 6 weeks for TAU or CAMS, followed by up to 8 weeks of CAMS or CC-DBT. It is assumed that weekly sessions align with typical CCCs. The counselor (interventionist) will be trained on CAMS and CC-DBT and will be evaluated for fidelity of implementation throughout the study. Length of time (e.g., student participant weeks in treatment) will be determined based on student participant responsiveness to their assigned treatment condition.

Except for the CC-DBT skills group and possibly other CCC therapy groups in the TAU condition, student participants will have no contact with other student participants, as this is an individualized treatment per each student participant.

Management of Student Participants in the Maintenance Phase. Student participants who are classified as responders during either stage 1 or stage 2 will end active study treatment and enter maintenance. Students may continue to receive CCC services during study maintenance. Students will continue to complete regularly scheduled IE assessments and remain in maintenance until the end of their study participation at 26 weeks. During the maintenance phase, the study team will contact students every four weeks. The four-week contact schedule will continue until their final assessment point. It is possible that students may experience a relapse in suicidality during the maintenance phase, which may be reported during the scheduled IE assessments, in response to a 4-week contact, or by the student spontaneously contacting a member of the CAMPUS trial clinical or research team. In these instances, students will be referred to their CCC for standard care. As noted elsewhere in this protocol (see section 6.5), treatments received outside of the study will be documented via the treatment history interview (THI).

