Treatment Adherence to CAMS and DBT. All treatment sessions will be digitally recorded. During the counselor training phase, counselors will participate in weekly remote group consultation/supervision (CAMS or DBT), which will be supplemented with individual site-level remote supervision as needed. A Standardized Operating Procedure (SOP) will be developed for certifying that counselors are adherent to CAMS and DBT treatment protocols. Following the training phase, two sessions will be randomly selected to be rated for adherence per DBT student, one from the first two sessions and one from the remaining sessions. A random sample of 10% of DBT skills group sessions will be selected for rating. For CAMS sessions in Stage 1, the first session will be rated for adherence and one other session will be randomly selected from the other sessions for adherence rating. For CAMS sessions in Stage 2, the first session after re-randomization into CAMS will be selected for rating and then one other session will be randomly selected. Feedback will be provided to counselor participants (but not in real time) and tallied in terms of percent of time counselor participants met minimal (DBT) or satisfactory (CAMS) adherence.

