9.3.2 ANALYSIS OF THE PRIMARY ENDPOINT(S)

Aim 1 analyses (Primary Aim) will compare and contrast the 4 pre-specified ATSSs embedded in the SMART design to determine whether one is clearly better or worse than the others with respect to mean suicidal ideation (SI) and suicide-related behaviors (NSSI and suicide attempts), which are the primary outcomes, at the end of 14 weeks of treatment. The data analysis method of Robins and colleagues^{160,161} will be used to contrast the 4 ATSSs based on reducing

suicide-related risk behaviors (SI, NSSI, and suicide attempts) to determine whether any of the interventions appear to be clearly better or worse than others. As part of the design, a student participant will contribute differentially to one or more of the 4 strategies (depending on the treatments to which he or she is randomized and whether he or she is a treatment responder), requiring a weighted comparison. Specifically, this analysis involves a weighted comparison of the cells A+B vs. A+C vs. D+E vs. D+F (see Table 8); the method by Robins and colleagues^{160,161} weights each student participant using the known randomization probabilities. Linear contrasts among the components of the ATSSs will be performed to further understand impact on efficacy. Similar analyses will compare the 4 strategies on the follow-up and secondary outcomes outlined above. Additionally, in response to reviewers' input, a composite outcome including suicidal ideation, suicide attempts, and NSSI will be derived. Death by suicide will be tallied but not included in the composite score. Song and colleagues¹⁶² provide a thorough discussion of the best ways to create composite scores, especially when dealing with a mixture of continuous and count outcomes. The analysis team will determine the best approach in the formation/derivation of the composite using the steps discussed by Song et al¹⁶². Similar analyses will compare the 4 strategies on the derived composite as outlined above.

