Raudenbush and Bryk¹⁶⁴ (p.125), we will treat counselor as a fixed effect. The primary contrast is between groups' difference in change from baseline to month 6 (end of acute treatment through Stage 1 and Stage 2 active treatment). The follow-up contrast at week 26 (12 weeks post-acute treatment) will also be examined in this and in all subsequent analyses. LMMs like the above for the primary outcome will be run for the secondary longitudinal outcomes: CAMS vs. TAU on CCAPS subscales (Depression, Anxiety, Academic Distress, Overall Distress), CGI-I and CGI-S (measured by IE), and cumulative GPA.

AIM 3 analyses will examine the relative effectiveness of switching to a more comprehensive suicide-focused treatment approach (e.g., CC-DBT) among those who do not respond sufficiently to Stage 1 treatments vs. a less intensive suicide-focused approach (e.g., CAMS). This analysis is a comparison of cells C+F (switch to CC-DBT) vs. B+E (switch or continue with CAMS) in Table 8. Both primary and secondary longitudinal outcomes outlined above will be examined using an LMM like that described above, but (a) including only the subset of responders to Phase 1 treatment, (b) defining group as switching to CC-DBT (cells C+F) vs. continuing or switching to CAMS (cells B+E), and (c) using monthly longitudinal outcomes from week 4 to week 24 (7 measurement occasions).

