Stage 2 analyses within Aim 8 focus on statistical contrast of the two randomized arms within Stage 2. Patients are the non-responders from Stage 1. Linear mixed models¹⁶³ (LMM, also known as random effects or growth curve models), fit with SAS PROC MIXED will be used to analyze the longitudinal data. LMMs use all available measurements, allowing student participants to have an unequal number of observations and producing unbiased parameter estimates if unobserved values are missing at random. The analysis will fit a LMM with fixed effects for the intercept, time, group, and a group-by-time interaction term, where group is an indicator of stage-one treatment (CC-DBT vs. CAMS as referent). The LMM will also include random effects for the intercept and time and an unstructured within-person correlation structure for the residual errors and will adjust for the following measures collected at baseline (pre-randomization): site, age, race, and clinical severity. Model diagnostics will be used to determine suitability of more parsimonious (e.g., autoregressive) correlation structures, and nonlinear (e.g., quadratic) effects for time. Complexity of the model and variance/covariance structures may be constrained by the available repeated measures. Counselor will be treated as a random effect which models potential correlation between student participants within a common counselor. If there is not sufficient variance, indicated by the reliability estimate of the random effect falling below 0.02 (a slighter lower threshold compared to Raudenbush and Bryk¹⁶⁴ (p.125), we will treat counselor as a fixed effect. The primary contrast is between groups' difference in change from Stage 2 randomization to end of Stage 2. Comparison of these findings will be to the results from the linear contrasts of the components of the ATS as described in Aim 1.

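### CC-DBT skills training may be given in groups while Stage 2 CAMS is individual, yet no planned analysis models skills-group clustering, so the CC-DBT vs CAMS standard error may be modestly understated

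*Combined protocol and SAP*

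**What the plan says.** **Treatment format.** The synopsis (1.1) gives CC-DBT as individual therapy plus "either a skills training group or individual skills training". Section 4.4 repeats that "skills training may be conducted individually or in group format", depending on participant flow and the point in the term. Groups are expected: section 6.2.1 sets an adherence rule, "A random sample of 10% of DBT skills group sessions will be selected for rating", and the consent check in 6.1.3 mentions a possible group for students assigned to DBT. CAMS is described in 4.4 as individual sessions. Section 6.1.6 says students have no contact with one another, "Except for the CC-DBT skills group and possibly other CCC therapy groups in the TAU condition". Section 4.4 says of TAU that it is mainly weekly individual therapy, "but it may also occasionally include group participation and/or medication referral".

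**Analysis.**
- Aim 1 (9.3.2): the weighted comparison "weights each student participant using the known randomization probabilities". No clustering is stated.
- Aim 2 (9.3.2) and both parts of Aim 8 (9.3.7): "Counselor will be treated as a random effect which models potential correlation between student participants within a common counselor". If the counselor variance is too small, "we will treat counselor as a fixed effect".
- Aim 3 (9.3.2): a mixed model of the Aim 2 kind, comparing cells C+F with B+E.
- Section 9.2 contains no ICC or design effect.

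No section mentions a skills-group term.

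**The concern.** Students who share a skills group for six weeks share a leader, peers and events, so their outcomes may be correlated. In Stage 2 this arises in CC-DBT and not in CAMS. A model that treats CC-DBT students as independent given their counselor then understates the variance of the CC-DBT mean, and a CC-DBT vs CAMS difference is declared somewhat too easily.

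The counselor term is not a substitute. It is an intercept shared by students in both arms, because the same counselors deliver all treatments. A skills group exists in one arm only and can draw its members from several counselors. Section 4.4 defends mixing telehealth and in-person delivery on the ground that it occurs in all arms. That defence is not available for skills groups in Stage 2.

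**Working it through.** **1. The plan's own figure.** Section 9.2 claims over 80% power for Aim 3 with 180 students in Stage 2 (90 per arm), d = 0.34, within-person correlation 0.60 and 2.5% type I error. Baseline adjustment gives an SD factor of √(1 − 0.60²) = 0.8, so the SE is 0.8 × √(2/90) = 0.1193 and 0.34/0.1193 = 2.851.
- One-sided 2.5%: Φ(2.851 − 1.960) = 81.4%, which reproduces the claim.
- Two-sided 2.5%: Φ(2.851 − 2.241) = 72.9%.

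The claim is thus matched by a calculation with no clustering. Sidedness is not stated for Aim 3; Aim 2 calls its 2.5% test two-sided, and I use two-sided for type I error below.

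**2. Effect of grouping on CC-DBT vs CAMS (C+F vs B+E).** Let m be group size, f the share of the arm treated in groups, and ICC the within-group correlation. All three are assumptions.
- Design effect in the CC-DBT arm: DE = 1 + f(m − 1)ICC
- True SE / unclustered SE, equal arms: R = √((1 + DE)/2)
- Actual type I error: 2(1 − Φ(2.2414/R))
- Power at the correct SE, from step 1 (one-sided): Φ(2.851/R − 1.960)

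| m | ICC | f | DE | R | Type I | Power |
|---|---|---|---|---|---|---|
| 3 | 0.02 | 0.5 | 1.02 | 1.005 | 2.6% | 81.0% |
| 3 | 0.10 | 1 | 1.20 | 1.049 | 3.3% | 77.6% |
| 5 | 0.05 | 1 | 1.20 | 1.049 | 3.3% | 77.6% |
| 6 | 0.05 | 0.5 | 1.125 | 1.031 | 3.0% | 79.0% |
| 6 | 0.10 | 0.5 | 1.25 | 1.061 | 3.5% | 76.7% |
| 6 | 0.10 | 1 | 1.50 | 1.118 | 4.5% | 72.2% |

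**3. Plausible group size.** Half of the 180 to 240 students entering Stage 2 gives 90 to 120 in CC-DBT. Over four primary sites and two recruitment years that is 90/8 ≈ 11 to 120/8 = 15 per site per year, some of them individually trained. This favours small to middling groups.

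**4. Does the counselor term absorb it?** With about 24 counselors at a time, 90 to 120 CC-DBT students is 3.75 to 5 per counselor position over the whole trial, so a concurrent group of 3 to 6 would usually span counselors. In a null simulation (90 per arm, groups of 6, ICC 0.10, 24 counselors unrelated to group), a nominal two-sided 2.5% test rejected 4.3% of the time ignoring clustering and 4.0% with counselor fixed effects, against 4.5% by formula.

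**5. Aim 1.** Take 120 responders and 60 students per Stage 2 cell under each Stage 1 treatment. With weights 2 (responders) and 4 (re-randomised), each strategy mean is half the responder mean plus half the cell mean.
- *ATS-1 vs ATS-2.* Cell A cancels, leaving ½(mean of C − mean of B). If groups mix C and F by chance, about half of a student's groupmates are in C, so DE = 1 + (m − 1)ICC/2. At m = 5, ICC 0.05: DE = 1.10, R = √(2.10/2) = 1.025, type I 2.9%. The excess is half of that in step 2.
- *ATS-2 vs ATS-4.* Groups shared by C and F also create a positive covariance between the two means. With chance mixing the extra variance and the covariance cancel almost exactly. If every group holds equal numbers from C and F, the C-minus-F variance is multiplied by 1 − ICC, and the whole contrast by (1 + 2(1 − ICC))/3 = 1 − 2·ICC/3. For ICC 0.02 to 0.10 the true SE is 0.7% to 3.4% smaller than the unclustered one.

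**6. Aim 2.** CC-DBT students are on both sides (C and F), so the same cancellation applies.

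**The case against.** A reader might infer that grouping occurs in CC-DBT only, that every CC-DBT contrast has too small a standard error, and that the error always favours CC-DBT. The documents do not support this.

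- *Other arms.* Sections 4.4 and 6.1.6 allow occasional groups under TAU, so students in cells D, E and F may have shared a Stage 1 group. The one-arm description is right only for CC-DBT vs CAMS in Stage 2.
- *Direction.* Step 5 shows that ATS-2 vs ATS-4 can be slightly overstated, and that ATS-1 vs ATS-2 carries about half the excess when groups mix cells.
- *Aim 1's criterion.* Section 9.2 sizes Aim 1 on a 90% probability of picking the best strategy, so a type I error figure does not describe that criterion.
- *Size.* Groups of 8 for the whole arm with ICC 0.10 would give a 16% larger SE and 5.4% type I error. The accrual figures in step 3 make that unlikely, and 4.4 offers individual training as an alternative depending on flow.
- *Counselor overlap.* Section 8.1 shows that study counselors deliver skills training. Where the group leader is also a member's individual counselor, the counselor term takes up part of the correlation. The documents do not say how often; the simulation assumed no link.

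All of these stand, and they limit the reach and size of the point. They do not supply a skills-group term for Aims 3 and 8, where the contrast is direct and the direction is clear if the ICC is positive.

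**Conclusion.** The omission is real and its effect is conditional. For CC-DBT vs CAMS in Stage 2 (Aim 3, called secondary in 9.3.1, and the exploratory Stage 2 part of Aim 8), the SE is understated if within-group correlation is positive and groups cut across counselors. Under groups of 3 to 6, ICC 0.02 to 0.10 and half to all of the arm grouped, the true SE is about 0.5% to 12% larger and type I error about 2.6% to 4.5% against a nominal 2.5%; groups of 5 with ICC 0.05 and the whole arm grouped give 3.3%. On the one-sided reading that reproduces the plan's power, 81.4% falls to between 81.0% and 72.2%. With ICC zero or all training individual, there is no effect.

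For Aim 1 no single direction can be claimed, and Aim 2 is only marginally affected by skills groups. The effect of any TAU groups cannot be sized from the documents.

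**What to change.** 1. Record a skills-group identifier for each CC-DBT student, and a group identifier for any TAU therapy group that participants share. Do this during the trial, since membership may be hard to reconstruct afterwards.
2. In Aim 3 and Aim 8 Stage 2, keep the counselor term and add a random effect for skills group that applies only to group-delivered CC-DBT, with Satterthwaite or Kenward-Roger degrees of freedom.
3. In Aim 1, use a variance clustered on treatment group that allows covariance between strategies sharing a group, with students not treated in a group as singletons.

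The cost is the identifiers, one model term and a change of variance estimator. The downside is slightly wider intervals and fewer degrees of freedom for CC-DBT vs CAMS. If groups turn out to be few or small, the results will hardly change.

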4.5 END-OF-STUDY DEFINITION

The end of the study for the CAMPUS Trial, is defined as completion of the Week 26 follow-up assessment shown in Table 1 Schedule of Activities (beginning on Page 16). Student participants

who terminate early will receive an end of study assessment identical to that required of participants who complete the entire protocol.

